Pilot data from our currently funded FRQS project focusing on cognition and AMD indicate correlations between sensory and cognitive variables in the expected directions insofar as individuals with faster reading speeds demonstrated better scores on the Montreal Cognitive Assessment^{57,58}. Given the information reviewed above, the logical direction for our investigation into the functional connection between LV and cognition is to examine the possible effects of reading rehabilitation on the cognitive abilities of LV patients over time. In order to dis-entangle the effects of visual and cognitive impairments in older adults, members of this research team have adapted cognitive tests so they can be administered to individuals with low vision^{59,60}. In parallel, we are also in the process of developing a vision-screening test that can be administered to individuals with various levels of cognitive impairment^{61,62}. This investigation will guide our future research efforts into the improvement of service provision in LV rehabilitation for the purpose of increasing the independence and health of older adults living with LV.

[figure not shown]
The objectives are to:

- Evaluate cognitive functioning and memory before, and 6 and 12 months after low vision reading rehabilitation using magnification in AMD patients, compared to those with dual (vision and hearing) impairments, and age-matched controls
- Correlate participant characteristics with all cognitive outcome variables in order to identify potential mediators, moderators or confounders

Hypotheses:

- Measures of reading effort (self-report and objective reading speed) will be statistically significantly reduced after participants have received strategies and tools to facilitate reading.
- Measures of reading behaviour will be negatively correlated with measures of reading effort (e.g., participants who report less effort will read a greater amount, more frequently and for longer)
- Individuals who demonstrate reduced reading effort and improved reading behaviour will demonstrate improved scores on cognitive tests after 6 months of having received rehabilitation strategies and tools, compared to those whose reading effort remains high or whose reading behaviour remains unchanged. These beneficial effects will be maintained after 12 months.
- Reading measures correlate with cortical thickness (CT) in the visual cortex;

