Sample Size: Effect sizes in vision rehabilitation in the past have ranged from approximately Cohen's $d = .20$ to 2.5 ³⁸. Since there are no existing effect size estimates for cognitive ability in the context of low vision rehabilitation, we are applying these values as a guide line: Using an average value of $d = 1.0$, and converting this value into variance accounted for ($r^2 = .20$ ¹⁰⁵), we can estimate a required sample size. Using a 3x3 (group x time point) within-between design for Analysis of Variance, power analysis using gPower¹⁰⁶ indicates that a sample size of $n = 141$ allows us to detect small effect sizes of .15 or greater, with an alpha of 0.05 and a desired power of .95. We expected an attrition rate of around 10% at each time point, given our previous research with older visually impaired adults^{107,108}. Therefore, a sample of $n = 200$ (to yield 150 patients, 50 controls) should be sufficient for our protocol. This goal is feasible given an average of 3000 new referrals to rehabilitation in Montreal per year.

Data Collection

Time 1 – Pre-Reading Rehabilitation: Participants will complete the questionnaires, hearing, reading and cognitive assessment components between their initial global intake exam and their first rehabilitation appointment. This period can span anywhere around 3 months, depending on waiting lists, and we will track whether any substantial changes in health occurred during this period that could influence eligibility or data collection.

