Time 2 – 6-Months and Time 3 – 12-Months Follow-Up: Six and 12 months after the initial rehabilitation appointment, the research assistant will meet with each participant (at home or in the lab, according to their preference) in order to repeat the experimental protocol, and all reading, cognitive and hearing measures will be administered each time. Throughout the period of the protocol, data from the rehabilitation chart will be extracted as it becomes available, with the final data collection concluding after the 12-month follow-up.

Statistical Analysis – Functional measures: To analyze these data, we will examine change in cognitive test scores from baseline over time using mixed-effects regression models, adjusting for level of vision and hearing impairment as fixed or random effects, and compare across sensory group (VI/DSI/Control). The analyses will include consideration of potential moderators or confounders (i.e., gender, age, education). In addition, we will calculate effect sizes, confidence intervals and Bayes Factors for main effects, interactions, and all post-hoc analysis.

When reflecting on the question of a control group we further consulted with the rehabilitation centres and discussed recruitment approaches and limitations; however, for practical and ethical reasons we are not able to withhold rehabilitation services from a possible comparison group, and waiting times are too varied across the centers and seasons of the year to allow for a waiting-list control group. As a result, we are proposing a quasi-experimental repeated-measures design with the intent to let the participants act as their own comparison across time points.

In addition, the data allow us to follow potential **exploratory avenues of analysis:**

- 1) If the recruited participants naturally divide into individuals whose reading effort was reduced and their reading activity has increased, versus those where we do not observe a change in reading behaviour, we can compare these two groups directly (e.g., while still considering their hearing status, or their gender)

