- 2) If no such clear division occurs but participants naturally distribute along a continuum of reading effort and reading behaviour variables, we can simply use the reading measure(s) as co-variables to test whether any/all of the reading effort measures emerge as significant co-variables, and examine whether cognitive scores improved over time across our three groups, after removing the effect of reading rehabilitation success.
- 3) Finally, we will use **latent factor analysis** to explore whether specific clusters of variables are specifically associated with improvements in cognitive functioning and/or improved reading ability. This analysis will be led by [name], together with [name] and [name].

Statistical Analysis - Cortical thickness:

Regression analyses of visual impairment on cortical thickness will be investigated at each vertex of the cortical surface using general linear modeling. Cortical thickness will be modeled as a function of group by controlling for the effects of age, gender, and education. Resulting clusters will be considered significant at $p < 0.05$ using a Monte-Carlo simulation approach. Similar analyses will be performed for cortical volume and cortical surface area, with the addition of total intracranial volume as a nuisance factor¹¹². In addition, a region-of-interest approach will be used to extract the CT values in specific regions of interest using the Destrieux cortical atlas¹¹³ in FreeSurfer. More specifically, we will compare across groups CT values extracted within specific regions of the visual cortex including the

[name]

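### Exploratory avenue 2, as literally worded, uses reading measures as plain covariates and does not isolate reading change, which is what the third hypothesis is about

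*Combined protocol and SAP*

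**What the plan says.** The third hypothesis in the protocol's list links change to change: "Individuals who demonstrate reduced reading effort and improved reading behaviour will demonstrate improved scores on cognitive tests after 6 months", compared with people whose reading effort or behaviour did not improve. Under Statistical Analysis – Functional measures, the main analysis is: "we will examine change in cognitive test scores from baseline over time using mixed-effects regression models". It compares the three sensory groups, adjusts for vision and hearing level, and considers gender, age and education. It contains no reading measure. The design is justified "with the intent to let the participants act as their own comparison across time points".

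Reading is linked to cognition only in the exploratory avenues that follow. Avenue 1 compares people whose reading effort fell and reading activity rose with those showing no change, if the sample splits that way. Avenue 2 is the fallback when it does not: "we can simply use the reading measure(s) as co-variables to test whether any/all of the reading effort measures emerge as significant co-variables". The same sentence then looks at cognitive improvement over time by group "after removing the effect of reading rehabilitation success". It does not say whether the covariate is reading at each visit, reading at baseline or change in reading. It names no centring, no within/between split and no reading-by-time term.

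The section on the 6- and 12-month follow-ups states that "all reading, cognitive and hearing measures will be administered each time", so reading is available as a time-varying covariate. The pilot data are reported as showing that "individuals with faster reading speeds demonstrated better scores on the Montreal Cognitive Assessment"; no coefficient is given.

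**The concern.** One coefficient for a time-varying covariate in a mixed model mixes two associations. One is between persons: do better readers score higher overall? The other is within person: does someone score higher at the visits where their reading is better? The third hypothesis needs the second. The pilot data already point to the first.

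A reading measure could therefore turn out significant in avenue 2 purely because good readers are good scorers, and the result could be taken as support for the third hypothesis. If change scores are modelled instead, with reading level as the covariate, the risk is the opposite: the level is only a weak proxy for reading change, and a real relation may be missed. These are alternative consequences of alternative models. They cannot both occur in one analysis.

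**Working it through.** **The plan's own figure.** The only related figure is the sample size: "allows us to detect small effect sizes of .15 or greater, with an alpha of 0.05 and a desired power of .95" with 141 participants. For the group-by-time interaction, lambda = N·m·f²/(1 − rho) = 141 × 3 × 0.0225/0.5 = 19.04, on 4 and 276 degrees of freedom, gives power 0.952. This assumes rho = 0.5 and sphericity, neither of which is stated. The figure reproduces and is not affected by this point.

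**Inputs.** From the Sample Size section: 200 enrolled (150 patients, 50 controls) and about 10% loss at each time point, so 200 × 0.9 × 0.9 = 162 completers, and 150 × 0.9 = 135 patients at six months. Assumed, because the documents do not give them: ICCs, the stable reading-cognition correlation r, the spread of reading gains, and equal halves of vision-only and dual-impairment patients (61, 61 and 40 controls among completers).

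**Visit-level reading on visit-level scores, no within-person link.** In a random-intercept model the coefficient is approximately w·b_between + (1 − w)·b_within. Take unit variances before gains, both ICCs 0.7, r = 0.3, and patient gains with SD 0.5 that are unrelated to cognition:

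- Weight on person means: 1/(1 + 3 × 0.7/0.3) = 1/8.
- Variance of person-mean reading: 0.7 + 0.3/3 + (122/162) × 0.25 × 4/9 = 0.884.
- Within-person sum of squares: 2 × 0.3 + (122/162) × 0.25 × 2/3 = 0.726.
- Between information: 3 × (1/8) × 0.884 = 0.331, so w = 0.331/(0.331 + 0.726) = 0.31.
- Between slope: 0.3 × 0.7/0.884 = 0.238. The blended coefficient is 0.31 × 0.238 + 0.69 × 0 = 0.074.
- Standard error: √(0.3/(162 × 1.057)) = 0.042, so z = 1.78 and the rejection probability is about 43%.

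Simulation of this scenario (1000 trials, REML, group-by-visit cells) gave a mean coefficient of 0.074 and rejection in 42.4%.

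Rejection of the plain covariate at nominal 5%, from simulation:

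| Stable r | 162 completers, ICCs 0.7, gain SD 0.5 | Range over all settings run |
|---|---|---|
| 0 | 5.3% | near 5% |
| 0.1 | 8.9% | 7-17% |
| 0.2 | 20.8% | 16-47% |
| 0.3 | 42.4% | 29-79% |
| 0.5 | 88.4% | 72-100% |

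The range covers ICCs of 0.5 to 0.85, completers only or all available data from 200, and gain SD from 0 to 1.0. The low ends from r = 0.2 upward come from gain SD 1.0 (16%, 29%, 72%). The high ends come from all available data with no variation in gains.

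With reading split into person mean and visit deviation, the deviation term rejected in 4.2-6.5% of trials over ten scenarios of 1000 trials (2.8-7.2% in smaller runs). Regressing cognitive change on reading change gave 4.6-6.4%.

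**Cognitive change score on reading level.** Rejection with no link was 4.0-6.6%, so there is no inflation. For power, with equal gains, corr(level, change) = √((1 − ICC)/2), which is 0.39 at ICC 0.7 and 0.32 at 0.8. For a true change-change correlation of 0.2-0.3, the level then correlates with cognitive change at 0.2 × 0.32 = 0.063 up to 0.3 × 0.39 = 0.116. Using the Fisher z approximation with n = 135, z = atanh(rho) × √132:

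- Reading level, equal gains: power 11-27%.
- Reading level, gain SD 0.5, ICC 0.7: corr(level, change) = 0.55/√(1.25 × 0.85) = 0.53, power 23-46%.
- Reading change: about 64% at 0.2 and 94-95% at 0.3.

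**The case against.** The strongest reply is that the plan never commits to the harmful model. Avenue 2 does not say level or change. The main model speaks of change from baseline, avenue 1 is framed in terms of change, and the closing words "after removing the effect of reading rehabilitation success" most naturally suggest a gain. With reading change as covariate, or with a cognitive change score as outcome, rejection stays near 5%. This stands: it is not established that the false-positive problem will occur. It does not remove the point. The closing words define no variable and belong to the group comparison rather than to the significance test. The literal wording enters the measures themselves.

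The size is also uncertain, and this stands too. The pilot correlation has no stated value and concerns the MoCA, which the plan treats as additional information beside its three cognitive domains. At r = 0.1 the inflation is modest. Avenue 2 applies when people spread along a continuum, so gains should vary, which lowers the rates. Planned adjustment for vision and hearing level, and consideration of age and education, were not simulated and would probably lower them further.

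Finally, avenue 2 is a conditional, exploratory fallback, and the Study Design section promises a pre-registered report in which the detail may be fixed. That limits the weight of the point. That report is not among the documents, so the wording here is what can be assessed.

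**Conclusion.** The point holds in a limited form. As literally worded, avenue 2 does not isolate reading change, so a significant reading covariate would not by itself bear on the third hypothesis. What follows depends on the model eventually used:

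- visit-level reading on visit-level scores gives the conditional false-positive rates tabulated above, which rest on assumed values of r, the ICCs and the spread of gains;
- reading level on cognitive change scores gives no inflation but low power;
- reading change as the covariate leaves no problem of this kind.

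A reader might infer that the trial will report a spurious link between reading gains and cognitive gains, or that its central test is invalid. The documents do not support either. The covariate form is left open, the avenue is labelled exploratory, nothing says a significant covariate will be reported as proof of the third hypothesis, and the main group-by-time model and the sample size are untouched. This is a cheap improvement, recommended with moderate confidence.

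**What to change.** State in avenue 2 which outcome is modelled and how reading enters:

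- If visit scores are the outcome, keep the group-by-visit terms and enter each reading measure as two terms: the participant's mean over visits and the visit's deviation from that mean.
- If cognitive change scores are the outcome, use the change in the reading measure over the same interval.
- If reading change is used with visit scores, include its interaction with time. A main effect alone avoids the inflation but does not directly test cognitive change.

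Base any statement about the third hypothesis only on the deviation or change term. Report the person-mean term separately as the cross-sectional association.

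The cost is one extra model term per reading measure, a sentence of wording, and a somewhat wider interval, because between-person information no longer feeds the coefficient. No new data and no change in sample size are needed.
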